### 9.3.3 Removal of Subjects From Therapy or Assessment

The investigator may discontinue study treatment or withdraw the subject from the study at any time for safety or administrative reasons. The subject may decide to discontinue study treatment or withdraw from the study at any time for any reason. The reason for discontinuation will be documented. If a subject discontinues study treatment, the subject will enter the Follow-up Period and complete protocol-specified off-treatment visits, procedures, PFS2 and survival follow-up unless the subject withdraws consent. The investigator should confirm whether a subject will withdraw from study treatment but agree to continue protocol-specified, off-treatment study visits, procedures, and PFS2 and survival follow-up, or whether the subject will withdraw consent. If a subject withdraws consent, the date will be documented in the source documents. The Discontinuation From Treatment CRF page will be completed indicating the primary reason for discontinuation and all other reason(s) contributing to the subject's discontinuation from treatment. In addition, the date of last dose of study drug will be recorded on the Study Drug Dosing CRF page.

During the Follow-up Period, subjects who have discontinued study treatment without disease progression should continue to have tumor assessments performed every 8 weeks until disease progression is documented, another anticancer therapy is initiated, or the data cutoff for primary analysis.

All subjects will be followed for survival until death, except where a subject withdraws consent or until the data cutoff for the primary analysis.

## 9.4 Treatments

### 9.4.1 Treatments Administered

Subjects randomized prior to Amendment 03 received 1 of the following 3 starting doses of lenvatinib: 24 mg/day, 20 mg/day, or 14 mg/day.

Beginning with Amendment 03, subjects will receive either 24 mg or 18 mg of lenvatinib orally QD. Study subjects, investigator site personnel, and the sponsor will be blinded to treatment assignment. Study subjects will be administered study drug in the form of two 10-mg capsules and two 4-mg capsules containing either lenvatinib or placebo (total of 4 capsules) to be taken with water each morning. Study drug is to be taken at approximately the same time each morning and may be taken in a fasting state or following a meal.

Doses will be packaged in blister cards totaling 24, 20, 18, 14, 10, 8, or 4 mg, as shown in [Table 3](#).

**Table 3 Study Treatments**

Total Dose (QD)	Capsule Allocation			
	10 mg Lenvatinib	10 mg Placebo	4 mg Lenvatinib	4 mg Placebo
24 mg	2	0	1	1
20 mg	2	0	0	2
18 mg	1	1	2	0
14 mg	1	1	1	1
10 mg	1	1	0	2
8 mg	0	2	2	0
4 mg	0	2	1	1

QD = once daily.

Each carton containing 2 blister cards will contain 16 doses (2 weeks plus 2 days allowing for a 2-day visit window). The investigator will have discretion to dispense up to 2 cartons simultaneously to a subject if it is appropriate for the subject to not return to clinic for 28 days.

#### 9.4.2 Criteria for Interruption of Treatment, Dose Reduction and Resumption of Treatment

Dose reduction and interruptions for subjects who experience toxicity will be made according to the guidelines provided in [Table 4](#). Dose reductions will occur in succession based on the subject's previous dose level (24, 20, 14, 10, and 8 mg QD or 18, 14, 10, 8, and 4 mg QD, respectively). Any dose reduction beyond 3 levels must be discussed with the sponsor. Once the dose has been reduced, it may not be increased at a later date.

**Table 4 Study Treatment Dose Reduction and Interruption Instructions**

Treatment-Related Toxicity a,b including hepatic injury and thromboembolic events	Management	Dose Adjustment

Grade 1 or Tolerable Grade 2		
	Continue treatment	No change (continue at Level 0)
Intolerable Grade 2c,d or Grade 3		
First occurrence	Interrupt until resolved to Grade 0-1 or baseline	Dose level -1 once a day (20 or 14 mg QD) (1-level reduction from previous)
Second occurrence (same toxicity or new toxicity)	Interrupt until resolved to Grade 0-1 or baseline	Dose level -2 once a day (14 or 10 mg QD) (1-level reduction from previous)
Third occurrence (same toxicity or new toxicity)	Interrupt until resolved to Grade 0-1 or baseline	Dose level -3 once a day (10 or 8 mg QD) (1-level reduction from previous)
Fourth occurrence (same toxicity or new toxicity)	Interrupt until resolved to Grade 0-1 or baseline	Stop Treatment or discuss possible dose level -4 with sponsor (8 or 4 mg QD) (1-level reduction from previous)
Grade 4e: Discontinue Study Treatment		

Note: For grading see Common Terminology Criteria for Adverse Events version 4.03. Collect all grades of adverse events, decreasing and increasing grade.

QD = once daily.

- a: A delay of study treatment for more than 28 days (due to treatment-related toxicities) will require a discussion with the sponsor before treatment can be resumed.
- b: Initiate optimal medical management for nausea, vomiting, and/or diarrhea prior to any study treatment, interruption, or dose reduction.
- c: Applicable only to Grade 2 toxicities judged by the subject and/or physician to be intolerable.
- d: Obese subjects with weight loss do not need to return to baseline weight or Grade 1 weight loss to restart lenvatinib. There should be no weight loss for at least 1 week, and subjects should be started at the lower dose. Normal body mass index should be used as a reference for future dose reductions.
- e: Excluding laboratory abnormalities judged to be non-life-threatening, in which case manage as Grade 3.

#### 9.4.2.1 Management of Hypertension

Hypertension is a recognized side effect of treatment with drugs inhibiting VEGF signaling. Investigators should therefore ensure that subjects enrolled to receive treatment with lenvatinib have BP of  $\leq 150/90$  mmHg at the time of study entry and, if known to be hypertensive, have been on a stable dose of antihypertensive therapy for at least 1 week before Cycle 1/Day 1. Early detection and effective management of hypertension are important to minimize the need for lenvatinib dose interruptions and reductions.

Regular assessment of BP should be conducted as detailed in Schedule of Procedures/ Assessments (Table 7). Hypertension will be graded using CTCAE v4.03, based on BP measurements only (and not on the number of antihypertensive medications).

If the subject's initial BP measurement is elevated (systolic BP  $\geq 140$  mmHg or diastolic BP  $\geq 90$  mmHg), the BP measurement should be repeated at least 5 minutes later. The mean value of 2 measurements at least 5 minutes apart is defined as one BP assessment. If the BP assessment (ie, the mean of the 2 BP measurements obtained at least 5 minutes apart) is elevated (systolic BP  $\geq 140$  mmHg or diastolic BP  $\geq 90$  mmHg), a confirmatory BP assessment should be obtained at least 30 minutes later by performing 2 measurements at least 5 minutes apart (to yield a mean value).

Lenvatinib should be withheld in any instance where a subject is at imminent risk to develop a hypertensive crisis or has significant risk factors for severe complications of uncontrolled hypertension (eg, BP  $\geq$ 160/100 mmHg, significant risk factors for cardiac disease, intracerebral hemorrhage, or other significant co-morbidities). Once the subject has been on the same antihypertensive medications for at least 48 hours and the BP is controlled, lenvatinib should be resumed as described below

Subjects with systolic BP  $\geq$ 160 mmHg or diastolic BP  $\geq$ 100 mmHg must have their BP monitored on Day 15 (or more frequently as clinically indicated) until systolic BP has been  $\leq$ 150 mmHg and diastolic BP has been  $\leq$ 95 mmHg for 2 consecutive treatment cycles. If a repeat event of systolic BP  $\geq$ 160 mmHg or diastolic BP  $\geq$ 100 mmHg occurs, the subject must resume the Day 15 evaluation until systolic BP has been  $\leq$ 150 mmHg and diastolic BP has been  $\leq$ 95 mmHg for 2 consecutive treatment cycles.

The following guidelines should be followed for the management of systolic BP  $\geq$ 140 mmHg up to  $<$ 160 mmHg or diastolic BP  $\geq$ 90 mmHg up to  $<$ 100 mmHg confirmed on repeat assessment after at least 30 minutes:

- Continue lenvatinib and initiate antihypertensive therapy, if not already receiving.
- Continue lenvatinib and increase the dose of the current antihypertensive therapy or initiate additional antihypertensive therapy.

The following guidelines should be followed for the management of systolic BP  $\geq$ 160 mmHg or diastolic BP  $\geq$ 100 mmHg confirmed on repeat assessment after at least 30 minutes:

- Continue study drug and institute antihypertensive therapy for subjects not already receiving this.
- For those subjects already on antihypertensive medication, the dose of the current agent may be increased, if appropriate, or one or more agents of a different class of antihypertensive should be added.
- If systolic BP  $\geq$ 160 mmHg or diastolic BP  $\geq$ 100 mmHg persists despite maximal antihypertensive therapy, then study drug administration should be interrupted and restarted at one dose level reduction only when systolic BP  $\leq$ 150 mmHg and diastolic BP  $\leq$ 95 mmHg and the subject has been on a stable dose of antihypertensive medication for at least 48 hours.
  - If systolic BP  $\geq$ 160 mmHg or diastolic BP  $\geq$ 100 mmHg recurs on the first dose reduction despite optimal management of hypertension with antihypertensive medications (either by dose increase or the addition of a different class of antihypertensive), then study drug administration should be interrupted and restarted at an additional dose reduction only when systolic BP  $\leq$ 150 mmHg and diastolic BP  $\leq$ 95 mmHg and the subject has been on a stable dose of antihypertensive medication for at least 48 hours.
  - If systolic BP  $\geq$ 160 mmHg or diastolic BP  $\geq$ 100 mmHg recurs on the second dose reduction despite optimal management of hypertension with antihypertensive medications (either by dose increase or the addition of a different class of antihypertensive), then study drug administration should be interrupted and restarted

at a third dose reduction dose only when systolic BP  $\leq 150$  mmHg and diastolic BP  $\leq 95$  mmHg and the subject has been on a stable dose of antihypertensive medication for at least 48 hours.

- Additional dose reduction should be discussed with the sponsor.

The following guidelines should be followed for the management of Grade 4 hypertension (life-threatening consequences):

- Institute appropriate medical management
- Discontinue study drug

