**Study Treatments**

Study subjects, investigator site personnel, and the sponsor will be blinded to treatment assignment. Study subjects will be administered study drug in the form of two 10-mg capsules and two 4-mg capsules of lenvatinib or placebo provided in a blister package totaling a dose of 24, 20, 18, 14, 10, 8 or 4 mg to be taken with water each morning. Study drug should be taken at approximately the same time each morning. Study drug may be taken in a fasting state or following a meal.

Study drug will be provided as follows for the 24-, 20-, 18-, 14-, 10-, 8-, and 4-mg doses:

Total Dose (QD)	Capsule Allocation			
	10 mg lenvatinib	10 mg placebo	4 mg lenvatinib	4 mg placebo
24 mg	2	0	1	1
20 mg	2	0	0	2
18 mg	1	1	2	0
14 mg	1	1	1	1
10 mg	1	1	0	2
8 mg	0	2	2	0
4 mg	0	2	1	1

Dose adjustments will be made according to the guidelines provided in the table below for management of intolerable toxicities.

Note: Refer to the relevant sections below for management of hypertension, proteinuria, hepatotoxicity, thromboembolic events, posterior reversible encephalopathy syndrome (PRES), and hypocalcemia.

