5.6.4 Vital Signs

Each parameter of vital signs assessments (diastolic and systolic BP, pulse rate, respiratory rate, temperature) and body weight will be summarized/plotted by visit (only those having results for $\geq 10\%$ of subjects) for the actual value observed and its change from Baseline. Hypertension, based on diastolic and systolic BP measurements, will also be summarized as shift from Baseline to worst postbaseline grade (see Table 3 for CTCAE grading).

Table 3 Blood Pressure Grading per CTCAE Version 4.03

Grade	Blood Pressure (mm Hg)	
	Systolic	Diastolic
1 (Prehypertension)	120 – 139	80 – 89
2 (Stage 1 Hypertension)	140 - 159	90 – 99
3 (Stage 2 Hypertension)	≥ 160	≥ 100

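### At a confirmed blood pressure of 160/100 mmHg or above, Protocol Section 9.4.2.1 supports both withholding and continuing study drug, and it is unclear whether Table 4 applies and how dosing restarts

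*Protocol*

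**What the plan says.** Protocol Section 9.4.2.1 (Management of Hypertension) contains two instructions that reach the same blood pressure.

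- **Withhold.** "Lenvatinib should be withheld in any instance where a subject is at imminent risk to develop a hypertensive crisis". The sentence goes on to include anyone with important risk factors for serious complications, and a pressure of 160/100 mmHg or higher stands first among its examples. The example carries no requirement that the pressure be confirmed, persist or have failed treatment. Dosing resumes after at least 48 hours on the same antihypertensive medication once the pressure is controlled, in the manner described further down.
- **Continue, then escalate.** For systolic BP ≥160 or diastolic BP ≥100 mmHg, confirmed at least 30 minutes later: "Continue study drug and institute antihypertensive therapy for subjects not already receiving this". For subjects already treated, the dose is raised or an agent added. Only if the pressure "persists despite maximal antihypertensive therapy, then study drug administration should be interrupted and restarted at one dose level reduction only when" it is at or below 150 systolic and 95 diastolic, with at least 48 hours on stable medication, does interruption come in.

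The Synopsis, under its own hypertension heading, carries both instructions in the same form.

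A third text may apply. Section 9.4.2 says "Dose reduction and interruptions for subjects who experience toxicity will be made according to the guidelines provided in" Table 4. For a first intolerable Grade 2 or Grade 3 treatment-related toxicity, Table 4 says "Interrupt until resolved to Grade 0-1 or baseline", then restart one level lower. Hypertension is graded on blood pressure alone, and SAP Table 3 (Section 5.6.4) puts ≥160 systolic or ≥100 diastolic at Grade 3. The Synopsis section on study treatments has a note, "Refer to the relevant sections below for management of hypertension, proteinuria, hepatotoxicity, thromboembolic events", that Section 9.4.2 lacks.

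**The concern.** An investigator who meets a first confirmed reading of 160/100 can point to protocol text for stopping the drug and to protocol text for carrying on. This is a safety threshold for an event that heads the list of Study 303 adverse events in Protocol Section 7.1 and that, with proteinuria, led most often to dose reductions there.

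The choice is lasting, because Section 9.4.2 does not allow a reduced dose to be raised again. Number of dose reductions and time to first dose reduction are secondary endpoints (Protocol Section 9.7.1.1.2, SAP Section 5.1.2), and dose intensity is reported under SAP Section 5.6.1. If sites read the text differently, these measures partly reflect local interpretation. The analysis could hardly separate that out: about 100 sites for 152 subjects is roughly 1.5 subjects per site (152/100 = 1.52), randomization is not stratified by site, and SAP Section 5.3.1 pools all centers.

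**Working it through.** The plan states no figure on this point, so the check is a comparison of texts. Take a subject with a first confirmed BP of 160/100 mmHg, which meets every trigger.

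| Text | Action at 160/100 | Restart condition | Dose on restart |
|---|---|---|---|
| 9.4.2.1, withhold paragraph | Withhold | Controlled BP, 48 hours on the same medication | Not stated; refers to the text below it |
| 9.4.2.1, stepwise guidelines | Continue and treat; interrupt only after maximal therapy fails | ≤150 and ≤95, 48 hours on stable medication | One level lower |
| Table 4, Grade 3 | Interrupt | Grade 0-1 or baseline | One level lower |

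**Pairwise comparison**

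1. Withhold against continue: a contradiction. The pressure named as a sufficient example for withholding is the one at which the guidelines continue the drug.
2. Continue against interrupt, both within the guidelines: no contradiction. Interruption is a later step that requires failure of maximal therapy.
3. Continue against Table 4: a contradiction only if Table 4 applies to hypertension. Section 9.4.2 makes no exception, and the Synopsis note implies one without saying so. The note alone cannot be decisive: it also lists proteinuria, hepatotoxicity and thromboembolic events, and those sections send the reader back to Table 4.
4. Restart after withholding: the paragraph refers forward, but every restart described there comes with a dose reduction and follows failed maximal therapy. Whether a subject withheld under the earlier paragraph returns at the same or a lower dose is therefore undefined.

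**Restart limits.** In SAP Table 3, Grade 2 is 140–159 systolic or 90–99 diastolic. A subject at 150/95 meets the guideline limit (150 ≤ 150, 95 ≤ 95) but is still Grade 2, so does not meet Grade 0-1. Table 4 would be met there only through its baseline alternative. That can matter, since screening pressures up to 150/90, themselves Grade 2, are allowed.

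**What one reading costs in dose.** With the sequences 24, 20, 14, 10, 8 mg and 18, 14, 10, 8, 4 mg, a first reduction takes 24 − 20 = 4 mg or 18 − 14 = 4 mg, that is 4/24 = 16.7% or 4/18 = 22.2% of the starting dose, with no way back. The gap between arms is 24 − 18 = 6 mg at the start, 20 − 14 = 6 mg after one reduction each, 14 − 10 = 4 mg after two and 10 − 8 = 2 mg after three.

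**Number affected.** Section 7.1 ranks hypertension by frequency at any grade. It gives neither the share reaching 160/100 nor the share for whom the readings would lead to different dosing, so no count follows.

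**The case against.** The strongest defense is that the texts form a hierarchy. The withhold sentence is about risk: the pressure is one example beside cardiac risk factors, intracerebral hemorrhage and co-morbidities, so it can be read as an exception for high-risk subjects, with the stepwise guidelines as the default. Table 4 covers treatment-related toxicity, and its heading names hepatic injury and thromboembolic events but not hypertension. The proteinuria, hepatotoxicity, thromboembolic and PRES sections each refer to Table 4. The hypertension section does not, and it has its own sequence up to Grade 4. The withhold paragraph also refers forward for resumption, and both restart texts in the section use 48 hours.

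Much of this stands. It makes the Table 4 conflict secondary and links the two restart texts in part. It does not remove the main contradiction, because the example names the pressure with nothing else required; a reader who applies it literally stops the drug where the guidelines continue it.

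Three stronger readings are tempting and not supported.

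- A reader might infer three equal, competing instructions within the hypertension section. Interruption there is conditional and follows from continuing.
- A reader might infer that a large share of both arms is affected. The Study 303 ranking gives no such proportion.
- A reader might infer that the primary safety count is distorted. Grading uses blood pressure only, so handling of the drug does not change the grade of the triggering event. SAP Section 5.6.2 counts subjects with a Grade ≥3 TEAE by Week 24, so a subject whose Grade 3 hypertension is recorded as a TEAE in that window counts under any reading.

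**Conclusion.** The point holds as an internal inconsistency. Section 9.4.2.1 and the matching Synopsis text give opposite dosing actions at a confirmed BP of 160/100 mmHg or above. Two lesser gaps go with it: whether Table 4 applies to hypertension is left to implication, and the restart conditions and restart dose are not uniform.

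The effect is inconsistent safety handling and extra variability in interruptions, number of dose reductions and time to first dose reduction. For an individual subject the readings can differ by a permanent 4 mg step in either arm. The total effect cannot be sized from the documents. That sites would in fact diverge is an inference from the wording.

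An effect on later exposure, and through it on response by Week 24 or on later adverse events, is possible but indirect. Both arms follow the same text under double-blinding, so the expected result is added noise; no directional bias in either primary endpoint is shown.

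**What to change.** Reconcile Protocol Sections 9.4.2 and 9.4.2.1, Table 4, and the corresponding Synopsis text so that each blood pressure level has one instruction and one set of restart conditions, including whether a subject withheld under the risk paragraph returns at a reduced dose. State in Section 9.4.2 whether Table 4 applies to hypertension. The clinical team decides the rule; the statistical request is only that there be one.

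The cost is protocol wording and a letter to sites. No change to sample size or analysis is needed. Because the criteria for major protocol deviations are to be set before database lock (SAP Section 5.2.3), they should also say which text dosing decisions at this pressure are measured against, so that a site is not marked as deviating for following one of two conflicting passages.

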#### 9.4.2.2 Management of Proteinuria

Regular assessment of proteinuria should be conducted as detailed in the Schedule of Procedures/Assessments (Table 7). Guidelines for assessment and management of proteinuria:

##### 1. Grading of Proteinuria:

- Grading according to CTCAE v4.03 will be based on the 24-hour urinary protein result. Management of lenvatinib administration will be based on the grade of proteinuria according to instructions contained in Table 4, “Study Treatment Dose Reduction and Interruption Instructions”.

##### 2. Detection and Confirmation

- Perform urine dipstick testing per the Schedule of Procedures/ Assessments (Table 7).
- A 24-hour urine collection (initiated as soon as possible and at least within 72 hours) or an immediate spot urine protein-to-creatinine ratio (UPCR) test is required in the following situations:
  - The first (initial) occurrence of  $\geq 2+$  proteinuria on urine dipstick while on study drug
  - A subsequent increase in severity of urine dipstick proteinuria occurring on the same lenvatinib dose level
  - When there has been a lenvatinib dose reduction and at the new dose level the urine protein dipstick result is  $\geq 2+$
- A 24-hour urine collection (initiated as soon as possible and at least within 72 hours) to verify the grade of proteinuria is required when an immediate spot UPCR is  $\geq 2.4$ .

##### 3. Monitoring

- Urine dipstick testing for subjects with proteinuria  $\geq 2+$  should be performed on Day 15 of each cycle (or more frequently as clinically indicated) until the results have been 1+ or negative for 2 consecutive treatment cycles.

#### 9.4.2.3 Management of Hepatotoxicity

Liver function tests (ALT, AST, bilirubin levels) should be monitored at baseline, every 2 weeks for the first 2 months and monthly thereafter, and as clinically indicated (see Schedule of Procedures and Assessments [Table 7]). If signs/symptoms indicating liver

injury occur, instructions contained in [Table 4](#), Study Treatment Dose Reduction and Interruption Instructions should be followed. Appropriate supportive care should be provided together with close monitoring. If hepatic failure occurs the study drug must be discontinued.

